1.5.10 Scan protocol

The patient will be positioned in a left sided-decubitus position or lithotomy position depending upon which is most comfortable for them. Once comfortable an ultrasound probe from a standard ultrasound machine with a scan frequency of 7.5MHz, and about the size of an adult male's index finger, is gently placed into the rectum and the prostate identified. The following images of the prostate will be obtained and saved onto the PACS system

During the ultrasound examination, the prostate gland will be scanned in a longitudinal and transverse plane from the apex to base, including seminal vesicles, and from right lateral border to

assigned to provide the consultation and biopsy as part of the standard care. Findings of the MRI will then be discussed with the patient and the patient's pathway will proceed as normal.

1.5.11 Data collection - Phase 1

Each participant will be given a unique study ID number. All images, cine loops and data for the study will be acquired and stored under this separate study ID. The data will be stored on the Hull Teaching Hospitals password protected picture archive and reporting system (PACS). A password protected database, stored in a password protected network drive of Hull Teaching Hospitals will hold the unique identifier number and will be used to record study data.

The lead researcher will randomly allocate a unique identifier number to two of the participating healthcare professionals. The reviewers will be randomly allocated to reduce bias as far as possible within a small team. Each reviewer will have their own unique identifier number known only to the lead researcher. The identity of the reviewers will be anonymised. The images and cine loops stored for the study will have no patient identifiable data on them. [Appendix 4](#) outlines the image acquisition and review pathway for phase 1 of the study.

1.5.12 Data assessment

The set of images and cine loops will be reviewed, in retrospect, by the assigned reviewers. The images and cine loop will be reviewed via a PACS workstation with monitor quality, and viewing conditions, as similar as possible to the ultrasound monitors and scan rooms. The save images will be scored using a 5-point scale, similar to the established PI-RADSV2 prostate reporting scoring system used to report MRI. This 5-point scale provides a score of the ultrasound appearance ranging from homogeneous and mid-grey (highly likely to be benign) through to heterogeneous and echo-poor (highly likely to be malignant). Any identified focal areas will be measured and the site documented dependent upon where in the gland the image was taken. Assessment of the presence of Colour flow Doppler will documented on a 3-point scale ranging from no colour Doppler signal evident to florid colour Doppler evident (signal fills the imaging sample box). The scoring system for the standard ultrasound and micro ultrasound images is provided in [Appendix 6](#) (standard) and [Appendix 7](#) (micro). Once reviewed, the scores submitted on the data collection forms will be uploaded onto the database by the lead researcher.

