1.4 Study phases

This study is being undertaken as a PhD research project but within the NHS care setting. The study will consist of four phases:

1.4.1 Phase 1:

In this initial phase, eligible men who have consented to participate will undergo a transrectal ultrasound examination with a standard ultrasound probe and, at the same attendance a transrectal ultrasound examination with a new and novel probe using 29MHz scanning frequency. The images obtained from this examination will be retrospectively compared with the MRI imaging that has been obtained as part of the standard care pathway. The images obtained will be reviewed by two

health care practitioners with experience in prostate imaging and the outcomes of these reviews compared to evaluate agreement levels.

1.4.2 Phase 2:

The second phase of the study will evaluate the use of multiparametric standard and micro ultrasound in the assessment of men who are on an AS or WW pathway. This phase the study will evaluate if there are any changes in the findings at repeat ultrasound examinations that can indicate disease progression. Eligible men, who have consented to participate, will again undergo a transrectal ultrasound examination with a standard ultrasound probe and, at the same attendance a transrectal ultrasound examination with a new and novel probe using 29MHz scanning frequency.

1.4.3 Phase 3:

The process and acceptability of implementing new interventions and technologies into everyday clinical practice is frequently overlooked following research trials. This third phase will explore the views of the health care practitioners, who have consented to participate, regarding the use and implementation of the proposed new technologies; skill mix between these professional groups will be required for successful long term practice. The participants will be recruited from differing professionals within the staff groups of Hull University Teaching Hospitals NHS Trust. An adapted survey tool, derived from normalisation process theory framework, will be used to better understand how and if the new, complex, multi-parametric ultrasound techniques can be implemented within the organisational setting of everyday routine practice. A baseline assessment of confidence in knowledge and skills related to prostate cancer evaluation using ultrasound will be made.

1.4.3.1 Staff training:

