1.5.9 Image collection

Once written consent has been obtained, the patient will be shown to a private changing area, directly adjacent to the ultrasound examination room and asked to change into a hospital gown. The patient will be escorted into the scan room for the procedure to be undertaken. A chaperone will be present with consent of the patient, as per standard clinical practice. A randomly allocated sonographer who has consented to participate in the study will be introduced and verbal consent obtain for the procedure to commence.

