1.5.14 Data analysis

Once the database is complete for each participant, the lead researcher will compare the:

- ultrasound scores
- ultrasound colour Doppler findings
- prostate volume size
- lesion size

The above criteria will be compared between both the standard and micro-US imaging, and then the standard and micro-US with both MRI and histology. An assessment of agreement will be undertaken to evaluate the concordance between the two reviewers of the same images (Ranganathan, Pramesh and Aggarwal 2017). The relationship between these pairs will be evaluated using Bland-Altman plots. Scores from the ultrasound reviews will also be evaluated to determine inter-and intra-operator agreement between the randomly allocated reviewers. The inter-rater reliability, both within and across subgroups of reviewers, will be assessed using the intra-class correlation coefficient or the Cohen weighted kappa test (de Raadt et al. 2021).

1.6 Study design and methodology – Phase 2

Men eligible for AS will be invited to participate in phase 2. A multi-parametric US examination will be undertaken as part of the AS monitoring regime. Men under AS have a prostate serum antigen (PSA) blood test and digital rectal examination every 6 months. A multi-parametric US examination will be undertaken at these appointments to minimise unnecessary health care interactions for the participants. The multi-parametric US examination will be performed blinded to the previous examinations and histology results. The images will be scored and then correlated with previous imaging scores and current PSA levels. Any changes will be indicated to the lead urologist and the patients will be offered MRI imaging to evaluate any changes using existing gold standard imaging.

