1.6.6 Participation and patient contact

Following consultation and treatment choice the eligible patients will be given an information leaflet about the study. The lead researcher will be informed of the patients who have been approached by the specialist nurse. The lead researcher will then contact the patient by telephone and invite them to participate in the study. The phase 2 recruitment pathway is provided in [appendix 3](#). Once verbal consent has been given, a mutually convenient appointment will be made and confirmed with an appointment letter.

The patient will attend for agreed appointment and a face to face consultation with the lead researcher will be undertaken to discuss the study and obtain written consent. The lead researcher will be blinded to the results of the MRI and any previous ultrasound image collection at this time to minimise undue coercion into the study, as in phase 1.

1.6.7 Image collection Phase 2

The [ultrasound examination](#) described and image collection for phase 2 is identical to that of [phase 1](#). The exception being that once the images have been collected and stored the patient will be free to leave; no further consultation, procedure or examination will be undertaken.

1.6.8 Data collection phase 2

The data collection of phase 2 is identical to that of [phase 1](#). Data collections forms utilised are attached in [Appendix 6](#) & [Appendix 7](#). The current standard and micro-ultrasound collected as part of phase 2 will be reviewed by two randomly allocated reviewers and scored as outlined above.

1.6.9 Data assessment phase 2

Once scored the documented criteria will be compared between both the standard and micro-US imaging collected during phase 2, and then compared with the previous standard and micro-US imaging [collected](#) during [phase 1](#).

1.6.10 Data analysis phase 2

The relationship between these pairs will be evaluated using Bland-Altman plots as per [phase 1](#). Scores from the ultrasound reviews will also be evaluated to determine inter-and intra-operator agreement between the randomly allocated reviewers. The phase 1 images and cine loop are the baseline data that all subsequent phase 2 examinations undertaken on that particular participant will be compared.

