1.10.2.1 Risk

There is minimal risk to patients participating in phase 2 of the study. A trans-rectal ultrasound examination of the prostate will be performed prior to any standard care being undertaken. Standard care includes a PSA blood test and a DRE. A multi-parametric US examination will be performed immediately following the regular DRE. It again will involve a probe being inserted into the rectum, images taken and stored for evaluation later. This will be repeated with the micro ultrasound probe. The probe will then be withdrawn and the patient attendance complete. Both examinations will take no more than 10 minutes in total.

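### The same reviewers score each man's standard and micro-ultrasound images, and the visible protocol does not mask one modality's reading from the other although the two are compared directly

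*Protocol*

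**What the plan says.** **Reading.** Protocol 1.5.11 stores all of a man's images and loops under one study ID and allocates reviewers once: "The lead researcher will randomly allocate a unique identifier number to two of the participating healthcare professionals". Section 1.5.12 continues: "The set of images and cine loops will be reviewed, in retrospect, by the assigned reviewers". For phase 2, 1.6.8 names both modalities: "The current standard and micro-ultrasound collected as part of phase 2 will be reviewed by two randomly allocated reviewers". Scores go on two forms, Appendix 6 for standard and Appendix 7 for micro-ultrasound. Each form has its own reviewer number, review date and scan date.

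**Acquisition.** Sections 1.4.1 and 1.4.2 name the standard probe first and then, "at the same attendance a transrectal ultrasound examination with a new and novel probe using 29MHz scanning frequency". The phase 1 scan protocol (1.5.10) opens with the standard probe: "Once comfortable an ultrasound probe from a standard ultrasound machine with a scan frequency of 7.5MHz". The phase 2 risk section (1.10.2.1) describes one probe examination and then says: "This will be repeated with the micro ultrasound probe". Section 1.6.7 makes image collection the same in both phases.

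**Blinding.** Section 1.5.1 blinds the phase 1 examination to the pre-biopsy MRI. Section 1.6 blinds the phase 2 examination to earlier examinations and histology.

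**Comparison.** Section 1.5.14 opens its comparisons with: "The above criteria will be compared between both the standard and micro-US imaging". Each modality is then set against MRI and histology. Section 1.6.9 repeats the standard-to-micro comparison in phase 2.

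**The concern.** Two imaging methods are to be compared on the judgement of readers who, as far as the visible text goes, may know what the other method showed in the same man. This is review bias. A reader who has just marked a suspicious area on one set of images is likelier to find it on the next, and likelier to pass a gland as normal after a normal first reading.

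Three results are exposed. Agreement between modalities would tend to look better than it is. A real difference between them would tend to shrink. The modality read second would borrow from the first, so its own agreement with MRI and histology would no longer be purely its own.

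A lesser issue is probe order. If the micro scan always comes second, the operator captures the micro images after already seeing the gland, so modality and order cannot be separated at capture.

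**Working it through.** **1. Is there any masking between modalities?** Section 1.1.2 defines the multi-parametric assessment as standard, Doppler and high-frequency imaging together. The blinding in 1.5.1 and 1.6 is attached to that whole examination, so it shields the examination from MRI, earlier scans and histology. It does not separate the two components that 1.5.14 compares. The visible text has no separate session, reading order or recoded ID by modality.

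**2. Are the readers the same?** Allocation in 1.5.11 is made once, with no separate allocation by modality. In phase 2, 1.6.8 places both modalities with two allocated reviewers.

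**3. Can the operator also score?** One sonographer is allocated to each man (1.5.9: "A randomly allocated sonographer who has consented to participate in the study will be introduced"). Phase 3 staff both scan and score (1.9.3), and so does the lead researcher (1.7.5). The forms number reviewers 1 to 6. Assume that the operator is one of these six and that two are drawn with equal chance. The operator would then score his or her own patient with probability 2/6, about one third, unless excluded.

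**4. How large could carry-over be?** The protocol gives no figure to reproduce on this point. Both models below use assumed inputs.

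*Linear pull.* Let the second score become S2' = (1 − w)·S2 + w·S1, with equal variances and true correlation r between modalities. Then

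corr(S1, S2') = [(1 − w)r + w] / √[(1 − w)² + w² + 2w(1 − w)r].

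With r = 0.50:
- w = 0.25: 0.625 / √0.8125 = 0.69
- w = 0.50: 0.75 / √0.75 = 0.87

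The mean difference becomes (1 − w) times its true value. The covariance of S2' with any reference, such as the PI-RADS score, becomes (1 − w)·cov(S2, ref) + w·cov(S1, ref), which is the blurring described above.

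*Copied readings.* Simulated 5-point scores (the scale in 1.5.12) with equal category frequencies and latent correlation ρ, where a fraction f of second readings repeats the first. Quadratic-weighted kappa between modalities:

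| ρ | f = 0 | f = 0.1 | f = 0.2 | f = 0.3 | Rise at f = 0.2 |
|---|---|---|---|---|---|
| 0.3 | 0.268 | 0.341 | 0.417 | 0.488 | 0.149 |
| 0.5 | 0.455 | 0.508 | 0.560 | 0.616 | 0.105 |
| 0.7 | 0.649 | 0.682 | 0.718 | 0.753 | 0.069 |

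**5. Would the data reveal it?** Section 1.5.4 sets phase 1 at 30 to 60 men. Across the cases in the table, the sampling SD of kappa is about 0.10 to 0.17 at 30 men and 0.07 to 0.12 at 60. A rise of 0.07 to 0.15 is of the same order, so it could not be told from chance after the event.

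**The case against.** - **Scoring as one set.** A reader might infer from 1.5.12 that both modalities are opened together and that the second score is always made knowing the first. The text does not say so. The separate, dated forms would permit separate readings. Appendices 4 and 5 are the image review pathways, and only their headings can be read here, so what they contain cannot be counted as absent. This objection stands against any claim that joint reading is planned. It does not remove the point, because a separate form does not by itself mask one result from the other.
- **Pairing.** A reader might infer that using both probes in the same man makes the comparison invalid for want of independence. It does not. A paired design suits an agreement analysis, and the issue is masking.
- **Probe order.** Study scores come from stored images. The gland is swept systematically in two planes and cine loops are reviewed, so order can act only through what the operator captures. This stands, and it makes order the weaker limb. The order is explicit only in 1.10.2.1. For phase 1 it is implied by 1.5.10 and 1.6.7.
- **Consequence.** A reader might infer that the trial could not tell whether micro-ultrasound adds anything. That goes too far. Each modality is also compared with MRI and histology, which carry-over could blur but not void. The primary objective (1.3.1) concerns multi-parametric ultrasound as a whole, and no objective is to show micro-ultrasound superior.
- **Magnitude.** The weights and copied fractions are assumed, and both models build assimilation in. They show possible size, not that carry-over occurs.

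**Conclusion.** The point holds in a limited form. The same reviewers receive both modalities, the visible text does not mask one reading from the other, and 1.5.14 compares them directly. The likely direction of any bias is towards overstated agreement and a hidden difference, with some blurring against MRI and histology. Its size is unknown: the kappa rise of 0.07 to 0.15 rests on an assumed 20% of copied readings, equal category frequencies and latent correlations of 0.3 to 0.7.

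This is a conduct rule that must be fixed before reading starts, because no later analysis can undo unmasked reading. The conclusion depends on Appendices 4 and 5 not already separating the readings. Fixed probe order is secondary. The change is a cheap improvement, and the sample size is unaffected.

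**What to change.** - **Sections 1.5.12 and 1.6.8:** have reviewers score standard and micro images from separate work-lists under recoded IDs, in random case order and in separate sessions. Lock the first form before the second modality is opened.
- **Section 1.5.11:** do not allocate a reviewer to a man they scanned, where the team allows. With six numbered reviewers, excluding one operator leaves five for two places.
- **Section 1.5.10, carried into 1.6.7:** alternate or randomise which probe is used first, and record the order.
- **If Appendices 4 and 5 already separate the readings,** state that in 1.5.12 instead.

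**Cost:** a longer reading schedule, more work-list administration and a simple order list. No extra scans, readers or participants are needed. In phase 2 the sessions must be timed so that the existing alerts to the urologist and the MDT (1.6.10 and 1.10.2.2) are not delayed. For that reason no fixed interval between sessions is prescribed here.

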1.5.13 Data collation

Once the reviewers scores have been uploaded onto the database, the lead researcher will review the clinical information taken as part of the standard care consultation. This will include the PSA level and documented DRE report. Both will be added to the database. The MRI report is undertaken

as part of the standard care pathway. The MRI PI-RADS score and documented site of abnormality will be recorded on the data base. The histology results of any prostate biopsies undertaken will also be reviewed and the histological Gleason score added to the database.

1.5.14 Data analysis

Once the database is complete for each participant, the lead researcher will compare the:

- ultrasound scores
- ultrasound colour Doppler findings
- prostate volume size
- lesion size

The above criteria will be compared between both the standard and micro-US imaging, and then the standard and micro-US with both MRI and histology. An assessment of agreement will be undertaken to evaluate the concordance between the two reviewers of the same images (Ranganathan, Pramesh and Aggarwal 2017). The relationship between these pairs will be evaluated using Bland-Altman plots. Scores from the ultrasound reviews will also be evaluated to determine inter-and intra-operator agreement between the randomly allocated reviewers. The inter-rater reliability, both within and across subgroups of reviewers, will be assessed using the intra-class correlation coefficient or the Cohen weighted kappa test (de Raadt et al. 2021).

1.6 Study design and methodology – Phase 2

Men eligible for AS will be invited to participate in phase 2. A multi-parametric US examination will be undertaken as part of the AS monitoring regime. Men under AS have a prostate serum antigen (PSA) blood test and digital rectal examination every 6 months. A multi-parametric US examination will be undertaken at these appointments to minimise unnecessary health care interactions for the participants. The multi-parametric US examination will be performed blinded to the previous examinations and histology results. The images will be scored and then correlated with previous imaging scores and current PSA levels. Any changes will be indicated to the lead urologist and the patients will be offered MRI imaging to evaluate any changes using existing gold standard imaging.

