[figure not shown]

A Proof of Concept Study Evaluating the Role of Emerging
Ultrasound Technologies in the Assessment and Monitoring
of Localised Prostate Cancer in Men on an Active
Surveillance Programme

Study Protocol: Evaluating the Role of Ultrasound in
Prostate Cancer (ERUP)

6th December 2021

Evaluating the Role of Ultrasound in Prostate Cancer Study (ERUP Study)

Full title of the research:

A proof of concept study evaluating the role of emerging ultrasound technologies in the assessment and monitoring of localised prostate cancer in men on an active surveillance programme.

Short title for this project:

Evaluating the role of ultrasound in prostate cancer

Lead researcher

[name]

Consultant Sonographer
Ultrasound, Hull Teaching Hospitals

Research team

[name]

Consultant Urologist
Urology, Hull Teaching Hospitals

[name]
[name]
[name]

Abstract

Research plan, study design and protocol

Summary of the study:

Active surveillance (AS) is becoming an increasingly common treatment option for men who have been diagnosed with localised low-grade prostate cancer (PCa). Low-grade disease is commonly noted by clinicians to be clinically insignificant cancer but remains a psychological burden to many men in this cohort. There is consensus that regular review is required for men on AS so that early treatment can be undertaken if there is disease progression, and to support men living with a cancer diagnosis. Some AS protocols, including NICE, advocate the use of MRI as a regular part of the monitoring pathway. Unfortunately, access to MRI for AS, within the current health care environment in the UK, is limited due to increasing demand for primary diagnostic examinations, particularly in the post Covid-19 recovery phase. Emerging technologies in ultrasound imaging may, however, add another diagnostic tool to monitor disease for patients on AS. This proof of concept study is to evaluate whether new multi-parametric ultrasound techniques can safely reduce the number of MRIs required for effective AS.

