1.1 Purpose and design

Across the UK prostate cancer is the most common cancer in men. Developments in magnetic resonance imaging (MRI), and the implementation of a targeted biopsy regime, have resulted in a considerable improvement in the detection of prostate cancer. The advent of robotic prostatectomy, and improvements in radiotherapy, have both lessened the post-treatment side effects but no treatment is without significant risk of complications.

1.1.1 Clinical context:

Prostate cancer can be present as an indolent low-grade cellular change to the tissue but with very little risk of this progressing to a metastatic life threatening disease. Despite the improved diagnostic capabilities, there remain a significant proportion of men in whom low-grade cancer is detected and consequent treatment options may present a higher risk to quality of life than the presence of the localised disease. NICE CG 131 (2019) recommends men are offered active surveillance (AS) or watchful waiting (WW) as an option for low-risk localised prostate cancer and for whom radical prostatectomy or radical radiotherapy is suitable should advancing disease be detected. Both AS and WW involve proactively monitoring the patient for signs of disease progression rather than undertaking treatment immediately. Patients on an AS pathway are deemed suitable for intervention and curative treatment should there be signs of disease progression; patients on a WW pathway usually have comorbidities that preclude curative treatment but they may benefit from palliative care if there is evidence of future progression. The Prostate Testing for Cancer and Treatment (ProtecT) (Hamdy et al. 2016) trial was established to gain a better understanding of the effectiveness of treatments, including AS, for prostate cancer. ProtecT (Hamdy et al. 2016) concluded that, at a median of 10 years, prostate cancer specific mortality was low regardless of the treatment assigned and that adopting an AS approach is reasonable to avoid life limiting side effects (Da Silva et al. 2017, Klotz et al. 2015).

However, despite the findings of the ProtecT trial (Hamdy et al. 2016) and the NICE guidance 131 (NICE 2019) there is currently no standard approach to AS due to the inequalities in capacity and availability of services in the NHS. It is, however, agreed that men on AS require regular tests which should include a combination of the following:

- Prostate Specific Antigen (PSA)
- digital rectal examinations (DRE)

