- MRI scans
- prostate biopsies – either transrectal random or transperineal template biopsy

The improvements in MRI imaging and reporting indicate that regular scans would add valuable information for patients under AS but capacity is significantly hindering this as an available application. An overview of the current clinical pathway for patients in the local region is provided as [appendix 1](#). This highlights the very real impact that capacity issues in MRI has on patient diagnostic pathways.

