1.3.2 Secondary objectives

Secondary objectives of this study are:

- to evaluate the diagnostic parameters of diagnostic ultrasound that can be utilised to assess disease within the prostate gland.
- To evaluate the diagnostic parameters of diagnostic ultrasound that can be utilised to assess disease progression within the prostate gland.
- To evaluate if the intra and inter operator variability in the assessment of ultrasound imaging parameters of the prostate gland can be investigated.
- To determine if a suitable standardise imaging protocol and reporting tool or model could be utilised in the reporting of transrectal ultrasound imaging of the prostate.
- To gain a better understanding of how new ultrasound technology and techniques can be implemented and embedded into clinical practice.

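### Phase 2 ties its MRI and biopsy check to a change on the ultrasound under evaluation, so missed progression, and with it the Summary's question of safely reducing MRIs, cannot be assessed

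*Protocol*

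**What the plan says.** **The question.** The Summary of the study says that the work is to "evaluate whether new multi-parametric ultrasound techniques can safely reduce the number of MRIs required for effective AS". A secondary objective in section 1.3.2 concerns the "diagnostic parameters of diagnostic ultrasound that can be utilised to assess disease progression within the prostate gland", and section 1.4.2 has phase 2 look for "any changes in the findings at repeat ultrasound examinations that can indicate disease progression". The formal aim (1.2) and primary objective (1.3.1) are softer: reliable, reproducible imaging and a viable tool.

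**The reference check in phase 2.** Under section 1.6, ultrasound scores are "correlated with previous imaging scores and current PSA levels", and when something has changed "the patients will be offered MRI imaging to evaluate any changes using existing gold standard imaging". Section 1.10.2.2 arranges MRI when the ultrasound raises concern, and biopsy when that MRI differs from baseline. Section 1.6.10 sends any change in ultrasound score to the consultant urologist and the next MDT; it does not mention MRI.

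**What every phase 2 man receives.** Sections 1.6 and 1.10.2.1 describe PSA and DRE as standard care, with ultrasound added every six months. Under section 1.6.7 the visit ends once the images are stored. Section 1.1.1 says that "men on AS require regular tests which should include a combination of the following", and its list includes MRI and biopsy. Of regular MRI it then says that "capacity is significantly hindering this as an available application".

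**What is compared.** Sections 1.6.9 and 1.6.10 compare standard with micro-ultrasound, new ultrasound with phase 1 ultrasound, and one image reader with another. Section 1.10.2.3 adds correlation with earlier MRI, and with histology if there is any.

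**The concern.** To say that ultrasound can safely replace some MRIs, one must know how often a man whose ultrasound is stable has in fact progressed. That is the false-negative side: sensitivity and negative predictive value (NPV) for progression. In the visible text, the only study-specified route to MRI or biopsy in phase 2 runs through a change or concern on the ultrasound itself. This is verification that depends on the index test. Men with stable ultrasound, who are the men in whom an MRI would be saved, have no planned reference result.

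If the Summary stands, a series of stable ultrasounds with no recorded progression could be read as evidence that MRI can be left out. That pattern would arise whether or not progression was being missed.

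**Working it through.** **Step 1. Could a stable man obtain a reference result some other way?**
- *PSA.* Section 1.6 mentions current PSA just before the trigger sentence, so on one reading a PSA change may also lead to MRI. Section 1.10.2.2 names only the ultrasound. A man stable on both still has no reference result.
- *Routine MRI or biopsy.* Either may happen, since section 1.1.1 lists both, but the same section says that capacity limits regular MRI.
- *Data capture.* Section 1.5.13 records PSA, DRE and MRI score for phase 1, and says "The histology results of any prostate biopsies undertaken will also be reviewed". Section 1.6.8 makes phase 2 data collection the same as phase 1, but phase 2 has no counterpart to section 1.5.13. No visible text says that later routine MRI or biopsy is captured for all phase 2 men.
- *Clinical course.* Recruitment may run to 18 months and imaging to 24, so follow-up is 24 − 18 = 6 months to 24 − 0 = 24 months. That is a weak substitute.

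**Step 2. What can be estimated.** The protocol gives no progression or flag rate and no derivation for the phase 2 maximum of 30 (section 1.6.2), so there is no stated figure to reproduce. Everything below is an assumption for illustration: N = 30, F men flagged and all verified, P = 3 confirmed, S = 30 − F stable and unverified.

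The yield among flagged men is P/F, which is estimable. For F = 6 it is 3/6 = 50%; for F = 15, 3/15 = 20%; for F = 24, 3/24 = 12.5%. The yield depends heavily on how the trigger is defined.

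**Step 3. What cannot be estimated.** Among verified men sensitivity is 3/3 = 100% by construction. Let x be the number of progressors among the S stable men. Then sensitivity = 3/(3 + x) and NPV = (S − x)/S, with x anywhere from 0 to S. At F = 6, S = 24:

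| x (unseen) | Sensitivity | NPV |
|---|---|---|
| 0 | 3/3 = 100% | 24/24 = 100% |
| 1 | 3/4 = 75% | 23/24 = 96% |
| 3 | 3/6 = 50% | 21/24 = 87.5% |
| 24 (extreme) | 3/27 = 11% | 0/24 = 0% |

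The recorded data are identical in every row. For F = 15 and F = 24 the extreme sensitivity floors are 3/18 = 17% and 3/9 = 33%.

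**Step 4. What captured routine results would add.** If m of the 24 stable men turn out to have a clear routine MRI or biopsy, the floors become 3/(27 − m) for sensitivity and m/24 for NPV. For m = 5 these are 3/22 = 14% and 5/24 = 21%; for m = 12 they are 3/15 = 20% and 12/24 = 50%.

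**Step 5. Precision if every stable man were verified.** With none missed among n, the exact 95% upper limit for the share of stable men who have progressed is 1 − 0.025^(1/n) two-sided, or 1 − 0.05^(1/n) one-sided.
- n = 24: 14.2% two-sided, 11.7% one-sided.
- n = 30: 11.6% two-sided, 9.5% one-sided.

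**Step 6. Trigger and action side by side.** Sections 1.6 and 1.6.10 act on any change, while section 1.10.2.2 acts on something of concern. The action is MRI in sections 1.6 and 1.10.2.2, and MDT review in section 1.6.10. Step 2 shows why this matters: the denominator F follows from it.

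**The case against.** The strongest reply is that this is a capped proof-of-concept study and that the safety claim sits in one Summary sentence. The formal aim and primary objective do not depend on it. Sections 1.10.1.3, 1.10.2.2 and 1.10.2.3 already say that the ultrasound is not yet diagnostic, and nothing in the protocol promises sensitivity or NPV. All of this stands. It limits the point to the Summary and to any reading of the progression objective that includes missed cases. It also shows that the Summary is out of step with the rest of the document.

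The progression objective also keeps real content. Several parameters are scored, so a man flagged on one may be a verified negative on another, and relative comparisons among verified men remain possible. Only the absolute miss rate is lost.

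Two stronger readings are tempting and are not supported. A reader might infer from the small numbers that size alone rules out any safety conclusion. The protocol states no threshold, and the answer turns on the one chosen and on the type of interval: for a limit below 10%, the two-sided calculation needs 36 verified stable men, but the one-sided needs 29 (ln 0.05/ln 0.90 = 28.4), which is within the maximum of 30. A reader might also take 11% as a likely sensitivity. It requires every unverified man to have progressed, which is implausible in a cohort that includes low-risk disease and PI-RADS 1 or 2 men, followed for at most 24 months.

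Finally, cross-tabulations usually belong in an analysis plan, and the phase 2 charts in Appendices 3 and 5 are not shown. A scheduled MRI in those charts would change the conclusion. An analysis plan alone would not, because it cannot supply results or records that the protocol does not arrange to collect.

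**Conclusion.** The point holds in limited form. On the visible text, phase 2 can estimate reproducibility, change over time, the yield of MRI after an ultrasound change, and relative performance among verified men. It cannot estimate missed progression, so whether MRI can be safely reduced is not answerable from it. The aim, the primary objective and the phase 1 comparison with MRI are not affected.

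The size can only be illustrated, because the protocol gives no rates. Under the assumed 6 flagged and 3 confirmed of 30, the data fit any sensitivity from the extreme floor of 11% up to 100%. Full verification would leave limited precision, but would make the question estimable. The conclusion rests on the Appendix 3 and 5 charts not scheduling a reference test for stable men. It should be fixed before results are interpreted.

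**What to change.** 1. **Summary.** Say that phase 2 addresses reproducibility, change over time and the yield of MRI after an ultrasound change, not whether MRI can be safely omitted. This brings it into line with sections 1.10.1.3, 1.10.2.2 and 1.10.2.3.
2. **Sections 1.6.8 to 1.6.10.** State that for every phase 2 man, whatever his ultrasound result, routine-care PSA, DRE, any MRI or biopsy and any move to treatment are extracted to the end of the study, extending the section 1.5.13 fields. Cross-tabulate these against ultrasound change and report how many stable men were verified.
3. **Trigger and action.** Reconcile sections 1.6, 1.6.10 and 1.10.2.2 on what sets off action (any change or a concern) and on what follows (MRI or MDT review). Which clinical rule applies is for the study team; none is proposed here.

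The cost is some record extraction and a few database fields, with no added MRI, biopsy or visit. Section 1.13 says that the consent forms allow the research team access to data, but their wording should be checked for follow-up records. The downside is a narrower stated claim, and a gap that is made visible but not closed.
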